14.2.21 Time to progression

[figure not shown]
Some studies might consider only death related to underlying cancer as an event which indicates progression. In this case the variable “Time to progression” might be used. TTP is defined as PFS except for death unrelated to underlying cancer.

Time to progression (TTP) is the time from date of randomization/start of treatment to the date of event defined as the first documented progression or death due to underlying cancer. If a patient has not had an event, time to progression is censored at the date of last adequate tumor assessment.

14.2.22 Time to treatment failure

This endpoint is often appropriate in studies of advanced disease where early discontinuation is typically related to intolerance of the study drug. In some protocols, time to treatment failure may be considered as a sensitivity analysis for time to progression. The list of discontinuation reasons to be considered or not as treatment failure may be adapted according to the specificities of the study or the disease.

Time to treatment failure (TTF) is the time from date of randomization/start of treatment to the earliest of date of progression, date of death due to any cause, or date of discontinuation due to reasons other than ‘Protocol violation’ or ‘Administrative problems’. The time to treatment failure for patients who did not experience treatment failure will be censored at last adequate tumor assessment.

14.2.23 Duration of response

The analysis of the following variables should be performed with much caution when restricted to responders since treatment bias could have been introduced. There have been reports where a treatment with a significantly higher response rate had a significantly shorter duration of response but where this probably primarily reflected selection bias which is explained as follows: It is postulated that there are two groups of patients: a good risk group and a poor risk group. Good risk patients tend to get into response readily (and relatively quickly) and tend to remain in response after they have a response. Poor risk patients tend to be difficult to achieve a response, may have a longer time to respond, and tend to relapse quickly when they do respond. Potent agents induce a response in both good risk and poor risk patients. Less potent agents induce a response mainly in good risk patients only. This is described in more detail by [Morgan \(1988\)](#).

It is recommended that an analysis of all patients (both responders and non-responders) be performed whether or not a “responders only” descriptive analysis is presented. An analysis of responders should only be performed to provide descriptive statistics and even then interpreted with caution by evaluating the results in the context of the observed response rates. If an inferential comparison between treatments is required this should only be performed on all patients (i.e. not restricting to “responders” only) using appropriate statistical methods such as the techniques described in [Ellis et al \(2008\)](#). It should also be stated in the protocol if duration of response is to be calculated in addition for unconfirmed response.

For summary statistics on “responders” only the following definitions are appropriate. (Specific definitions for an all-patient analysis of these endpoints are not appropriate since the status of patients throughout the study is usually taken into account in the analysis).

Duration of overall response (CR or PR): For patients with a CR or PR (which may have to be confirmed the start date is the date of first documented response (CR or PR) and the end date and censoring is defined the same as that for time to progression.

[figure not shown]
The following two durations might be calculated in addition for a large Phase III study in which a reasonable number of responders is seen.

Duration of overall complete response (CR): For patients with a CR (which may have to be confirmed) the start date is the date of first documented CR and the end date and censoring is defined the same as that for time to progression.

Duration of stable disease (CR/PR/SD): For patients with a CR or PR (which may have to be confirmed) or SD the start and end date as well as censoring is defined the same as that for time to progression.

14.2.24 Time to response

Time to overall response (CR or PR) is the time between date of randomization/start of treatment until first documented response (CR or PR). The response may need to be confirmed depending on the type of study and its importance. Where the response needs to be confirmed then time to response is the time to the first CR or PR observed.

Although an analysis on the full population is preferred a descriptive analysis may be performed on the “responders” subset only, in which case the results should be interpreted with caution and in the context of the overall response rates, since the same kind of selection bias may be introduced as described for duration of response in [Section 14.2.23](#). It is recommended that an analysis of all patients (both responders and non-responders) be performed whether or not a “responders only” descriptive analysis is presented. Where an inferential statistical comparison is required, then all patients should definitely be included in the analysis to ensure the statistical test is valid. For analysis including all patients, patients who did not achieve a response (which may have to be a confirmed response) will be censored using one of the following options.

- at maximum follow-up (i.e. FPFV to LPLV used for the analysis) for patients who had a PFS event (i.e. progressed or died due to any cause). In this case the PFS event is the worst possible outcome as it means the patient cannot subsequently respond. Since the statistical analysis usually makes use of the ranking of times to response it is sufficient to assign the worst possible censoring time which could be observed in the study which is equal to the maximum follow-up time (i.e. time from FPFV to LPLV)
- at last adequate tumor assessment date otherwise. In this case patients have not yet progressed so they theoretically still have a chance of responding

Time to overall complete response (CR) is the time between dates of randomization/start of treatment until first documented CR. Similar analysis considerations including (if appropriate) censoring rules apply for this endpoint described for the time to overall response endpoint.

14.2.25 Definition of start and end dates for time to event variables

Assessment date

[figure not shown]
For each assessment (i.e. evaluation number), the **assessment date** is calculated as the latest of all measurement dates (e.g. X-ray, CT-scan) if the overall lesion response at that assessment is CR/PR/SD/UNK. Otherwise - if overall lesion response is progression - the assessment date is calculated as the earliest date of all measurement dates at that evaluation number.

Start dates

For all “time to event” variables, other than duration of response, the randomization/ date of treatment start will be used as the start date.

For the calculation of duration of response the following start date should be used:

- Date of first documented response is the assessment date of the first overall lesion response of CR (for duration of overall complete response) or CR / PR (for duration of overall response) respectively, when this status is later confirmed.

End dates

The end dates which are used to calculate ‘time to event’ variables are defined as follows:

- Date of death (during treatment as recorded on the treatment completion page or during follow-up as recorded on the study evaluation completion page or the survival follow-up page).
- Date of progression is the first assessment date at which the overall lesion response was recorded as progressive disease.
- Date of last adequate tumor assessment is the date the last tumor assessment with overall lesion response of CR, PR or SD which was made before an event or a censoring reason occurred. In this case the last tumor evaluation date at that assessment is used. If no post-baseline assessments are available (before an event or a censoring reason occurred) the date of randomization/start of treatment is used.
- Date of next scheduled assessment is the date of the last adequate tumor assessment plus the protocol specified time interval for assessments. This date may be used if back-dating is considered when the event occurred beyond the acceptable time window for the next tumor assessment as per protocol (see [Section 14.2.26](#)).

Example (if protocol defined schedule of assessments is 3 months): tumor assessments at baseline - 3 months - 6 months - missing - missing - PD. Date of next scheduled assessment would then correspond to 9 months.

- Date of discontinuation is the date of the end of treatment visit.
- Date of last contact is defined as the last date the patient was known to be alive. This corresponds to the latest date for either the visit date, lab sample date or tumor assessment date. If available, the last known date patient alive from the survival follow-up page is used. If no survival follow-up is available, the date of discontinuation is used as last contact date.
- Date of secondary anti-cancer treatment is defined as the start date of any additional (secondary) antineoplastic therapy or surgery.

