7.1.7 Follow-up for survival

Upon completion of the 150-day safety follow-up or disease progression follow-up, all patients (except for those in Japanese safety run in) will be followed for survival via a phone call, email or letter, every 12 weeks until any of the following (whichever occurs first): death, withdrawal of consent, loss to follow-up or at least 24 months from the first dose of study treatment. Antineoplastic therapies or tumor directed surgical procedures initiated during the survival

follow-up period must be recorded on the Antineoplastic therapies since discontinuation of study drug eCRF.

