14.2.20 Overall survival

All patients should be followed until death or until patient has had adequate follow-up time as specified in the protocol whichever comes first. The follow-up data should contain the date the patient was last seen alive / last known date patient alive, the date of death and the reason of death (“Study indication” or “Other”).

Overall survival (OS) is defined as the time from date of randomization/start of treatment to date of death due to any cause. If a patient is not known to have died, survival will be censored at the date of last known date patient alive.

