2.6 Analysis supporting secondary objectives

2.6.1 Efficacy objectives

The secondary objective is to assess the efficacy of NIR178 in combination of PDR001 using ORR per iRECIST, and other efficacy measures including disease control rate (DCR), duration of response (DOR), progression free survival (PFS) and 2 year overall survival (OS) by both RECIST v1.1 and iRECIST for solid tumors, by PCWG3 guidance (see Protocol Appendix 5) for mCRPC, and by [Cheson et al \(2014\)](#) for DLBCL.

These efficacy endpoints will be summarized for all the treatment groups contributing to the analysis of primary efficacy objective (see [Section 2.1](#) general analysis conventions).

ORR:

Overall response rate (ORR) is defined as the proportion of patients with best overall response (BOR) of immuno-related complete response (iCR) or immuno-related partial response (iPR), as per local review and according to iRECIST (see Protocol Appendix 3 for details) for solid tumors.

ORR as per iRECIST will be provided for each treatment indication along with corresponding 95% confidence interval (CI).

DCR:

DCR is the proportion of patients with a best overall response of CR, PR or stable disease (SD). DCR will be summarized by treatment indication with accompanying 95% confidence intervals.

OS, PFS and DOR:

OS is defined as the time from date of start of treatment to date of death due to any cause. If a patient is not known to have died, OS time will be censored at the date of last contact. The 2 year OS rate is the proportion of patients with at least 2 years of OS.

PFS is defined as the time from start of treatment date to date of the first documented disease progression or date of death, whichever happens first. If a patient has not had the event at the date of analysis cut-off, PFS will be censored at the time of the adequate tumor assessment before the cut-off.

For patients with a confirmed CR or confirmed PR, the DoR is the time from date of first documented response (CR or PR) to date of first documented progression or death due to underlying cancer, whichever happens first. If progression or death has not occurred at the date of analysis cut-off, then DoR will be censored at the date of last adequate tumor assessment before the cut-off.

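### Protocol 14.2.25 gives two conflicting dates of last contact, and the SAP censors overall survival at that date without saying which applies

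*Protocol*

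**What the plan says.** - Protocol 14.2.20 censors a patient without a recorded death at the last date known alive: "If a patient is not known to have died, survival will be censored at the date of last known date patient alive".
- Protocol 14.2.25 opens its last-contact bullet in the same sense and says how to find the date: "This corresponds to the latest date for either the visit date, lab sample date or tumor assessment date". It then prefers the date on the survival follow-up page where there is one, and closes: "If no survival follow-up is available, the date of discontinuation is used as last contact date".
- The same section fixes what discontinuation means: "Date of discontinuation is the date of the end of treatment visit".
- SAP 2.6.1 uses the second term: "If a patient is not known to have died, OS time will be censored at the date of last contact". The SAP does not define it, and the list of end dates in SAP 5.4.4.2 omits it.
- SAP 2.6.1 also states: "The 2 year OS rate is the proportion of patients with at least 2 years of OS".
- Survival follow-up starts late. Protocol 7.1.7 sets its start: "Upon completion of the 150-day safety follow-up or disease progression follow-up, all patients (except for those in Japanese safety run in) will be followed". Before that, Protocol 7.1.5 plans safety contacts at 30, 90 and 150 days. Protocol 7.1.6 plans scans every 8 weeks to week 40 and every 12 weeks after that, for patients who stop without progression.

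**The concern.** A patient can stop treatment, be seen alive at safety contacts or scans, and be lost before any survival page is completed. For that patient the two parts of the bullet give different censoring dates, and the SAP does not choose between them.

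If the closing sentence is applied, known survival time is removed from living patients only. Deaths during follow-up keep their true date, because 14.2.25 takes them from the study evaluation completion page as well as the survival page. Whether a patient's time is cut back then depends on whether the patient lived, so the censoring is informative. At stake are the OS curve, its median and landmarks, and the 2-year OS rate, which is a named secondary endpoint. OS and progression-free survival (PFS) dates for the same patient may also disagree.

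**Working it through.** The documents give no OS sample size, event count or power (Protocol 10.9 is marked not applicable), so there is no plan figure to reproduce.

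**1. Which way the date moves.** Let A be the latest of all visit, lab and scan dates, and B the end-of-treatment (EOT) visit. The EOT visit is itself a visit, so A ≥ B always. The closing sentence therefore either changes nothing or moves a living patient's date earlier. Read literally, the last two sentences of the bullet (survival page if there is one, otherwise EOT) cover every patient, which leaves the latest-date sentence nothing to do.

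**2. One patient.** Cycle 1 Day 1 is day 1. Treatment stops for an adverse event, with the EOT visit at week 16: 16 × 7 + 1 = day 113. The week-32 scan shows progression: 32 × 7 + 1 = day 225. The patient is then lost with no survival page. If the last infusion was at week 12 (day 85), the 150-day safety follow-up runs to day 85 + 150 = 235, so the scan falls inside it.

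| | Day |
|---|---|
| PFS event | 225 |
| OS censored, latest-date sentence | 225 |
| OS censored, closing sentence | 113 |

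The closing sentence ends OS follow-up 112 days before an event that shows the patient was still alive.

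**3. Effect on Kaplan-Meier.** S(t) = ∏(1 − d/n) over death times. The deaths d are unchanged and each n is the same or smaller, so no factor can rise. The curve is strictly lower once another patient dies between a reset date and the true last contact.

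Take an illustrative group of 10, in months: deaths at 3, 5, 7, 9, 11 and 13; two alive at 24; two alive at 10 and 12, whose EOT visits were at 2 and 4.

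- Latest-date sentence, 12 months: 9/10 × 8/9 × 7/8 × 6/7 × 4/5 = 0.480; 24 months: × 2/3 = 0.320.
- Closing sentence, 12 months: 8/9 × 6/7 × 5/6 × 4/5 × 3/4 = 0.381; 24 months: × 2/3 = 0.254.

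**4. Size by simulation.** None of these assumptions comes from the documents. OS is exponential with median 9 or 12 months. Time on treatment is exponential with median 3 months. A share q of patients has no survival page and is last seen 0 to 8 months after EOT. The rest are followed to 24 months. There were 1,500 runs per setting. The table shows n = 30; each cell gives the latest-date result, then the closing-sentence result.

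| q | 12-month OS, median 9 | 12-month OS, median 12 | Estimated median, true 12 |
|---|---|---|---|
| 0% | 0.396, 0.396 | 0.499, 0.499 | 12.7, 12.7 |
| 10% | 0.400, 0.391 | 0.501, 0.492 | 12.4, 12.1 |
| 20% | 0.401, 0.382 | 0.501, 0.481 | 12.3, 11.7 |
| 40% | 0.394, 0.350 | 0.499, 0.454 | 12.4, 10.9 |

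At n = 10 the falls in 12-month OS are 0.8 to 0.9 points at 10%, 1.9 to 2.1 at 20% and 4.4 at 40%. In no run was the closing-sentence curve the higher one at 12 months. A second simulation, with median OS 8 months and patients leaving 1 to 5 months after EOT, gave 0.352 to 0.344 at 10% and 0.353 to 0.337 at 20%.

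**5. The 2-year proportion.** Suppose a patient stops at month 20 and is alive at the 150-day contact, about month 25. Protocol 7.1.7 asks for survival follow-up to at least 24 months from first dose, so a survival page is not clearly required. Under the closing sentence OS is censored at month 20, and this known 2-year survivor is not counted. One such patient costs 1/10 = 10 points in a group of 10, or 1/30 = 3.3 points in a group of 30.

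Such patients should be rare. With median treatment 3 months and last contact 3 months after EOT, the EOT visit must fall between months 21 and 24. That probability is 0.5^(21/3) − 0.5^(24/3) = 0.0078 − 0.0039 = 0.4%, before allowing for the share without a page.

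**The case against.** The correct rule is already in the protocol. The bullet opens with it, 14.2.20 states it for OS, and 14.2.36 handles the last date known alive and the date of last contact as one item. SAP 2.6.1 uses the term without adopting the closing sentence. A programmer who follows the definition creates no bias, and the derivations sit in a dataset specification (SAP section 1) that is not among these documents. This stands: the fault is a contradiction left open, and the documents do not show which sentence was programmed.

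The affected group may also be small. Protocol 7.1.7 starts survival follow-up after the safety or the progression follow-up, so a patient still being scanned beyond 150 days may already have a survival page. Patients who transfer to another study have no follow-up after EOT (Protocol 7.1.5.1), so EOT is their true last contact. Data after full withdrawal of consent are excluded (SAP 2.2.7). These points narrow the group but do not remove patients lost between EOT and the first survival contact.

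The shift is also small against sampling error. At n = 30 and 50% survival the standard error is √(0.25/30) = 0.091, or about 9 points. That is fair, but the shift goes in one direction only and costs nothing to remove.

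A reader might go further and infer that the plan's OS estimate is certainly too low, or that it yields an impossible OS shorter than PFS. The documents do not support either. The first needs the closing sentence to govern and some patients to lack a survival page, and neither is established. On the second, an OS censoring date before a PFS censoring date is an awkward record but not a logical impossibility. The progression case in the working is the clearer anomaly, because it shows the patient alive after the OS censoring date.

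**Conclusion.** The contradiction is real and worth correcting. SAP 2.6.1 rests OS censoring on a term that Protocol 14.2.25 defines in two incompatible ways. If the closing sentence is applied, the direction is certain: the OS curve is equal or lower, never higher. An OS censoring date can then precede the same patient's documented progression, and a patient known alive past 24 months can be missed in the 2-year proportion.

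The size is conditional. It is zero if every living patient with post-treatment contacts has a survival page. Under the exponential assumptions, 12-month OS falls by about 1 point at 10% without a page and about 2 points at 20%. The effect on the 2-year proportion should usually be slight, though one patient matters in a group of 10. OS is secondary and descriptive, so the primary response-rate analysis, the futility rule and the success rule do not change.

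**What to change.** Delete the last sentence of the last-contact bullet in Protocol 14.2.25. Since the EOT visit already counts as a visit, nothing is lost. In SAP 2.6.1, state that patients not known to have died are censored for OS at the latest date known alive, on or before the cut-off, from any collected source: survival page, safety follow-up contact, visit, lab sample, tumor assessment or dosing record.

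The cost is one sentence in the SAP and a small programming check. The dates are already collected, and the only effect on results is somewhat longer OS follow-up for some patients. If the protocol is not amended again, the SAP sentence is enough, provided it says that it replaces the closing sentence of the protocol bullet.

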14.2.26 Handling of patients with non-measurable disease only at baseline

It is possible that patients with only non-measurable disease present at baseline are entered into the study, either because of a protocol violation or by design (e.g. in Phase III studies with PFS as the primary endpoint). In such cases the handling of the response data requires special consideration with respect to inclusion in any analysis of endpoints based on the overall response evaluations.

It is recommended that any patients with only non-measurable disease at baseline should be included in the main (ITT) analysis of each of these endpoints.

Although the text of the definitions described in the previous sections primarily relates to patients with measurable disease at baseline, patients without measurable disease should also be incorporated in an appropriate manner. The overall response for patients with measurable disease is derived slightly differently according to [Table 14-6](#).

Table 14-6 Overall lesion response at each assessment: patients with non-target disease only

Non-target lesions	New Lesions	Overall lesion response
CR	No	CR
Non-CR/Non-PD ¹	No	Non-CR/non-PD
UNK	No	UNK
PD	Yes or No	PD
Any	Yes	PD

¹ As defined in [Section 14.2.8](#).

In general, the **non-CR/non-PD response** for these patients is considered equivalent to an SD response in endpoint determination. In summary tables for best overall response patients with only non-measurable disease may be highlighted in an appropriate fashion e.g. in particular by displaying the specific numbers with the non-CR/non-PD category.

In considering how to incorporate data from these patients into the analysis the importance to each endpoint of being able to identify a PR and/or to determine the occurrence and timing of progression needs to be taken into account.

For ORR it is recommended that the main (ITT) analysis includes data from patients with only non-measurable disease at baseline, handling patients with a best response of CR as “responders” with respect to ORR and all other patients as “non-responders”.

For PFS, it is again recommended that the main ITT analyses on these endpoints include all patients with only non-measurable disease at baseline, with possible sensitivity analyses which exclude these particular patients. Endpoints such as PFS which are reliant on the determination and/or timing of progression can incorporate data from patients with only non-measurable disease.

